## Waiver of Consent/Authorization

Indicate if you are requesting any of the following consent waivers

**Waiver of consent for use of records that include protected health information (a HIPAA waiver of Authorization)**

No

**Waiver or alteration of consent**

No

**Waiver of documentation of consent**

Yes

**Waiver of parental consent**

No

## Consent Procedures

**Is eligibility screening for this study conducted under a different IRB protocol?**

Yes

**Indicate NYSPI IRB #**

NYSPI IRB# 4436R

**Describe Study Consent Procedures**

1. Baseline Evaluation For potential patients contacting the STARS clinic or the Division on Substance Abuse at the Albert Einstein College of Medicine (DOSA), a standardized telephone interview is conducted at the first call. Prospective participants who do not present with immediate exclusion criteria are scheduled for a first screening visit. For patients already enrolled in the Next Step program at DOSA, screening may be arranged for patients deemed eligible by their counsellors, or after the patient has voluntarily initiated contact with the investigators. The screening process consists of a psychiatric diagnostic evaluation and a medical evaluation of the candidate to rule out any condition that may make participation in this study hazardous. The consent procedure for the baseline evaluation differs between the two sites. For patients enrolled through the STARS clinic, they must first read and agree to the general screening consent (NYPI

IRB# 4436R) describing the evaluation process in detail. For patients enrolling through DOSA, the screening process is included in the consent form for the study (Einstein IRB# 2014-3568). The screening process begins with completion of the following forms: locator form; demographic form, drug history questionnaire, concomitant medication form. The locator form indicates the patient's name, address, phone number, as well as names, addresses and phone numbers of family members and close friends, along with a permission to contact them. The demographic form records information about education, marital status, employment, income, social support, housing, gender and racial category. The drug history questionnaire reviews lifetime use of drugs by category, as well as any previous treatment attended. The psychiatric diagnostic evaluation follows, conducted by a member of the research staff (LCSW, CASAC, MD, PhD) trained in the administration of the Mini International Neuropsychiatric Interview (MINI; Lecrubier et al., 1997), a treatment/drug use history, and a Hamilton Depression Scale – 25 (Williams, 1988). The evaluation is conducted by a research psychiatrist (MD). It includes a psychiatric and medical review of systems, a mental status examination, a review of inclusion/exclusion criteria, and of the diagnostic evaluation. A consensus diagnosis is reached, which must include cocaine dependence, and not include any exclusion diagnoses. The MD then conducts the medical evaluation, including: medical history, review of systems, physical examination including vital signs, olfactoscopic examination of the nasal cavity, screening blood test (chem-20, CBC, urinalysis, urine toxicology, urine pregnancy test for women patients), and an electrocardiogram. The Scent test is conducted at this point. When completed, and the laboratory reports received, the assembled information is reviewed by the principal investigator or a research MD familiar with the study protocol. This information is reviewed against the inclusion/exclusion criteria of the study to determine eligibility to participate. For control participants, the screening process is the same as described for cocaine-dependent patients. For potential control participants entering through the STARS clinic, they will sign the screening consent form (IRB# 4436R). Those entering through DOSA, they will sign the study consent form for control participants (Einstein IRB# 2014-3568) 2. Informed Consent For patients from DOSA, they signed the consent form for the study at the time of screening. If the patient is found eligible to participate in the research study, they will be informed of this, and arrangements will be made with them (and with their counselor if applicable) to begin. For patients from the STARS clinic not meeting any exclusion criteria, we inform the patient about their eligibility to participate. If the patient agrees to participate, a consent appointment is set. The consent form for the study is presented to the patient to read. After reading, the patient answers a consent quiz to verify their understanding of the study they are about to begin. For control participants entering through DOSA, they will have signed the consent form written for control participants at the time of screening. For control participants entering through the STARS clinic, they will sign the consent form for control participants.

**Indicate which of the following are employed as a part of screening or main study consent procedures**

✓ Consent Form

**Waiver of Documentation of Consent**

**Would the consent form signature be the only link between the subject's identity and the**

---

**research data?**

Yes

**Is breach of confidentiality the main study risk?**

No

**Type in the name(s) not found in the above list**

**Study Procedures**

**Describe the procedures required for this study**

**Design Overview:**

This is a 2 phases, 7-weeks, prospective, double-blind, placebo-controlled, randomized clinical trial of comparing intranasal oxytocin to placebo in cocaine-dependent patients. The principal aim of the study is to examine if intranasal oxytocin can reduce the relapse risk. Cocaine-dependent and control patients will be recruited through IRB-approved advertising in public media, and from the STARS clinic of the Division on Substance Abuse at the New York State Psychiatric Institute, and the Division on Substance Abuse at the Albert Einstein College of Medicine. Prior to the 6-week outpatient phase, cocaine-dependent patients will be required to become abstinent. To achieve this, patients will opt for either an inpatient or an outpatient approach. During the inpatient approach, patients will be hospitalized at the New York State Psychiatric Institute (5-South) for 7 days to establish abstinence, participate in the stress challenge over 2 separate days which evaluates baseline stress sensitivity, investigate if oxytocin can exert an acute effect on stress parameters, and begin on randomized medication (IN oxytocin 24 IU/day vs. IN placebo). There will not be a placebo lead-in.

Table 1 presents an overview of phase 1 for cocaine-dependent and control patients.

see up-loaded table 1.

---

Because of professional, personal, or financial reasons, some patients may choose *the outpatient abstinence-induction procedure*. During this week, patients will need to attend the clinic on three consecutive days and provide a negative urine toxicology for cocaine at each visit. Following this, they must complete all the study procedures prescribed in the in-patient Phase 1 procedure: essentially the stress challenges as described in section 4A3 below. If a patient cannot remain abstinent during this week, the patient will be offered another attempt to become abstinent during following week and complete the phase 1 procedures. If a patient cannot achieve abstinence during either week, then the inpatient phase will be mandatory for continued participation. If the patient cannot do this, we will offer referrals for treatment in another setting.

Control patients will participate only in phase 1. They will not be hospitalized, but the structure of the testing will be such as to reproduce the conditions under which the cocaine-dependent patients will be tested. When the two consecutive days of testing are completed, their participation ends. These will be matched for age and gender.

Phase 2 follows to study the effects of intranasal oxytocin on relapse risk to cocaine use after abstinence is induced. This phase of the study will be carried out identically at the STARS clinic, or at the Division on Substance Abuse at Albert Einstein College of Medicine. During this phase, patients must attend the clinic three times a week. At these visits, the randomized medication will be taken under supervision of research staff, from a bottle kept at the research site. On the days when the patient is not at the research site, the medication is taken as instructed from an at-home bottle. Compliance with at-home administration will be monitored by a single-blind weighing of the at-home bottle at each visit. At each visit, vital signs, adverse events, urine toxicology, and drug use are reviewed. At one visit, the patient will meet with a counselor for compliance enhancement therapy. At another visit, the patient will meet with a research MD for ratings, monitor progress, and review side-effects.

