### *1.1 Neuropeptides, Vasopressin, Oxytocin: basic concepts.*

The history of neuropeptides begins with VP and OT. Du Vigneaud and his team deduced the structure of VP and OT, and synthesized each in 1954 (du Vigneaud, 1954). These peptides are old in phylogeny (going back 500 million years), have evolved together, are found in all vertebrates, and are early joint regulators of homeostasis; which required that the effect of one could counterpoise the effect of the other (Van Kesteren et al., 1992). OT and VP are synthesized within neurons from a single precursor: then, a cascade of processes determine its biological activity through size, form, and derivation of the end product, generating peptides with different, and at times, opposite effects (de Wied et al., 1993).

VP is the hormonal regulator of water homeostasis (Arimura et al., 1967). With Angiotensin, it governs drinking behavior (Severs et al., 1977). The hormone OT regulates parturition and lactation (Higuchi et al., 1986). It also promotes sexual, reproductive, social, and nurturing behaviors (Pedersen et al., 1979), on which VP exerts mostly a temporizing effect (de Wied et al., 1993). This intricate webbing of behavioral and physiological effects is a feature of hypothalamic neuropeptides. Another feature is reflected in their effect on single neurons: VP and OT can exert lasting influences (Kombian et al., 2002) on neurons at CNS sites controlling homeostasis (Buijs et al., 1983). For example, OT or VP affect 2nd messenger systems (Manning et al., 2008), influence the effects or the release of primary neurotransmitters such as glutamate (Joels and Urban, 1982; Van den Hooff and Urban, 1990), and can generate ionic currents (Dreifuss and Raggenbass, 1992) that induce Long-Term-Potential, an inducible neuronal activity that underlie behavioral adaptations and learning (Teyler and Discenna, 1987). Many of these effects outlast the functional half-lives of OT or VP.]

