**Phase 3 involves the repeat to the DDAVP stress challenge and a repeat salivary cortisol collection.**

Table 2 schematizes the structure of the whole protocol.

see uploaded Table 2

---

Week 1, phase 1: In-hospital phase, cocaine-dependent patients.

The purpose of the in-hospital phase is to allow abstinence to begin, and provide an environment amenable to stress sensitivity testing. Patients from either sites can be admitted to the General Research Unit on PI-5 for this phase, during which the following procedures will take place:

1) Establish controlled abstinence.

2) Complete baseline assessments, including Time Line Follow-Back (Litten & Allan, 1992) to quantify drug use, Cocaine Craving Scale (Weiss et al., 1997), Clinician Global Impression-Observer (Guy, 1976), Perceived Stress Scale (Cohen et al., 1983), Hamilton Depression Scale-25 items (Williams, 1988).

3) Upon the 1st negative urine toxicology for cocaine, we will collect baseline salivary cortisol samples at these approximate times: 8-9am, 11-12pm, 2-3pm, 5-6pm.

4) Stress Challenges. These consist of two tests performed on separate days in counterbalanced order, as illustrated below. The test itself will be performed in the Biological Studies Unit. Patients will have breakfast in the morning prior to testing.

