**measurements are repeated at specified time points.**

5) After baseline stress testing is completed, begin randomized administration of intranasal Oxytocin 20 IU per day in the morning, for each remaining day of phase 1. This will serve also as an opportunity to train patients on how to administer intranasal solutions. The steps are as follows: 1) exhale through the nose, head bent forward; 2) while inhaling, spray once into one nostril; 3) repeat step 1 & 2 for the other nostril; 4) repeat steps 1 to 3 again to reach the daily dose of 24 IU of randomized medication. The patients will be instructed by a member of the research staff to ensure proper technique and optimal absorption of the medication. The Oxytocin solution is stable at room temperature for one month after being opened. Nonetheless, the manufacturer recommends that the bottle be kept refrigerated between uses and we will recommend this to the patients as well. Its stability should ensure that transportation to the clinic should not cause degradation, provided it is not exposed to extreme heat (> 100 Fahrenheit), direct sunlight, or frozen.

Phase 1, control participants.

The purpose of Phase 1 for control participants without psychiatric, medical, or addiction disorders is to test their stress sensitivity with the same procedure as cocaine-dependent patients. This is to study if stress dysregulation is more prevalent among cocaine users than normal controls, and to study if vasopressin-based stress mechanisms bear some specificity to the stress dysregulation observed in cocaine-dependent patients.

For control participants, the procedure will be carried out over two days as outpatients. They will be instructed to present themselves between 9 to 10 am on a testing morning, having eaten breakfast. A saline lock will be inserted, and a 2-hour habituation period will follow before testing begins at approximately 1 pm. The procedure will be the same as described for cocaine-dependent patients, and will be administered in counterbalanced order (**see above, stress procedures**). Completion of phase 1 ends their participation in this study.

Phase 1, week 1, cocaine-dependent patients, outpatient version.

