This procedure is based on our previous experience acquired during protocol NYSPI IRB 6013 (mifepristone study for cocaine dependence) with patients who cannot participate in the inpatient procedure. Over a period of 7 days, not counting Saturdays and Sundays, a participant will have to produce at least three consecutive cocaine negative urine toxicologies at daily visits. Once abstinence is established the phase 1 procedures begin (Table 1), with verification of negative toxicology before each testing day. Randomized medication will begin after completion of all the physiological tests.

---

If a urine toxicology test emerges positive for cocaine once Phase-1 procedures have begun, the testing will stop. The patient can then attempt another period of seven days to reach abstinence, complete the baseline testing, and begin randomized medication. If abstinence cannot be reached during this two-week window, the patient will be offered to carry out phase 1 as an inpatient. If the patient cannot participate as an inpatient, referrals to other treatment options will be offered.

Phase 2, outpatient phase, week 2 to 7, cocaine-dependent patients only

During this phase in which only cocaine-dependent patients participate, they will continue randomized medication while participating in a structured program to support and promote continuing abstinence and completion of the study.

For patients continuing at the STARS clinic and DOSA at Waters Place ([name]), the structure of the program during this phase will be as follows:

- 1: Patients continue to receive intranasal Oxytocin (24IU/day) vs. intranasal placebo. During their visits to either clinic, they will administer the randomized medication under supervision from a bottle kept at the clinic. Each witnessed administration will be recorded. Since they "self-administer" the medication, it can be witnessed by any member of the research team.

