Study Assessments: (Table 1). **Physiological tests:** 1) *urine toxicology:* this will be estimated qualitatively at every visit by dipstick (Iscreen™, 9 drugs) which indicates the presence of cocaine, amphetamine, metamphetamine, cannabis, methadone, morphine, oxycodone, barbiturate, benzodiazepine. 2) *stress sensitivity testing:* as outlined in table 2, it is performed on two separate days, [in counterbalanced order.] Day 1: an endocrine challenge with IN DDAVP 80IU (de Goeij et al., 1991). After establishing baseline ACTH secretion, serum samples are taken at time points extending to 90 minutes. The DDAVP challenge is also repeated at the end of phase 2, to see if ACTH secretion is affected by 6 weeks of IN OT administration. Day 2 tests if pretreatment with IN OT treatment can acutely dampen the effect of DDAVP on ACTH secretion. After baseline is measured before and after IN OT, serum samples for ACTH are taken at time points extending to 90 minutes. Serum samples are spun, frozen at -20 Celsius, packed in dry ice, and shipped to the Nathan Kline Laboratory in Orangeburg, NY. 3) Medical monitoring: week 2,4,6: Na, K, Cl, CO3, spot cortisol, β-HCG for women. **Clinician Interviews:** 1) TLFB (Litten and Allan, 1992; baseline, each visit in phase 2). This is an adaptation of the alcohol TLFB, which estimates cocaine use in the past 30 days at baseline, and is then repeated at every visit with the aid of a calendar to obtain a day-by-day registry of cocaine use during phase 2. 2) CGI-O, (Guy, 1976; baseline, weekly during phase 2) the severity and improvement scales measure the overall clinical status of the subject and change from baseline. 3) BAS (Chaplin et al., 2010). This scale is used during stress sensitivity testing. Research staff rate participants on 13 items of behavior relating to arousal during the stress challenge. 4) Adverse event form is a check-list of side effects experienced by participants; 5) HamD, (Williams, 1988; baseline, each wk in phase 2). Estimates 25 depression symptoms. **Self reports:** 1) PSS (Cohen et al., 1983; baseline, weekly during phase 2) measures monthly situations in a subject's lives deemed stressful. Ten questions are scored between 0 (never) to 4 (very often). Modified, it will be administered weekly during phase 2, [and will include a open-ended question inquiring about any adverse life event in the past week.] 2) *Subjective ratings of cocaine craving, depression, anxiety, stress during stress testing (Likert scale 0 to 10, 10 = worse), performed during stress sensitivity testing.* 3) CCS (Weiss et al., 1997) 3-item questionnaire rating cravings for cocaine on a scale of 0 (none) to 9 (Strong).

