3.4.3. Intent to Treat/ Dropouts and missing data: All primary analysis will be on Intent-to-Treat (ITT) sample, i.e. all subjects from COC and CON groups in Phase 1 (50 per arm) and all subjects randomized to OT and PBO groups in Phase 2 (25 per arm). [In Phase 1, we expect little attrition. Measures as described (3.4.1) will provide usable data after 2 days of measurements. For phase 2, we anticipate an attrition rate of 30%, leaving approximately 18 completers per arm.] If a patient drops out during Phase 2, the maximum number of consecutive abstinent days achieved in the trial will be considered as primary outcome. The inferences from analyses with missing data are considered valid provided that they are "missing at random" (Little and Rubin 1987). One can assume either parametric or semi-parametric models for missingness (Diggle and Kenward 1994; Kenward 1998; Liu et al 1999; Rotnitzky et al 1998). Inferences from various models of missingness provides a measure of the efficacy estimate from each models.

3.4.4. Significance testing and preliminary analyses: All tests for main effects will be performed at two-tailed significance $\alpha=5\%$. Before performing specific analyses (described below), we will examine all variables for outliers and normality. Demographic variables (ethnicity, gender, age) and baseline measures in the groups will be described in terms of means, standard deviations, proportions and 95% confidence intervals. The covariates (Section 3.4.1) will be included if they are found to affect outcome measures.

Hypotheses:

Primary Aim 1 [Phase 1]: The goal of primary aim 1 is to investigate the effect that both IN DDAVP and OT have on stress sensitivity. **Primary Aim 1a, hypothesis 1:** IN DDAVP will be associated with greater secretion of ACTH and subjective ratings in cocaine dependent patients compared to control patients. **Primary Aim 1b, hypothesis 2:** IN OT treatment will significantly reduce the secretion of ACTH and subjective ratings associated with IN DDAVP in cocaine dependent patients compared to control patients. The differences based on the outcomes specified in hypotheses 1 and 2 between the subjects in COC and CON groups will be examined using parametric or non-parametric matched sample test.

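### The Phase 1 analysis ignores the counterbalanced test order, and the available text fixes the between-test interval for controls but not for patients (minor)

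*Protocol*

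**What the plan says.** On order, the Protocol (Study Procedures, in-hospital phase, item 4) says of the patients' stress challenges: "These consist of two tests performed on separate days in counterbalanced order". For controls (Phase 1, control participants) it says: "The procedure will be the same as described for cocaine-dependent patients, and will be administered in counterbalanced order". The SAP's description of the study assessments agrees.

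On spacing, the Design Overview says of controls: "When the two consecutive days of testing are completed, their participation ends". Of inpatients it says that they will "participate in the stress challenge over 2 separate days which evaluates baseline stress sensitivity", with no gap given. For outpatients whose testing is stopped by a positive toxicology, the outpatient version of Phase 1 says: "The patient can then attempt another period of seven days to reach abstinence, complete the baseline testing, and begin randomized medication". The Design Overview also states that control testing is meant to mirror the conditions of patient testing.

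On analysis, SAP 3.4.4 assigns both Aim 1 hypotheses to a "parametric or non-parametric matched sample test". The covariates in SAP 3.4.1 are demographic and cocaine-use variables; neither test order nor interval is among them. SAP 3.4.1 defines the Aim 1b outcome as the within-person difference between the two tests and labels them day 1 and day 2, although the order is counterbalanced.

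On persistence, Background 1.1 closes its account of single-neuron effects with: "Many of these effects outlast the functional half-lives of OT or VP". Background 1.4 says that intranasal peptides are measurable in cerebrospinal fluid for hours.

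**The concern.** The desmopressin-alone test is the whole outcome for Aim 1a and one of the two terms in Aim 1b. In about half the participants it follows an oxytocin session.

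There are two consequences. First, any general difference between a first and a second session, such as novelty or habituation, is balanced on average by the counterbalancing, but it stays in the error variance because the analysis does not use order. Second, if some oxytocin effect lasted to the next session, the desmopressin-alone response would be altered in the oxytocin-first half only. Counterbalancing does not cancel that.

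If the interval also differed between patients and controls, the carry-over could differ by group, and group is the contrast that both aims test. The plan gives no reason for taking carry-over to be zero, and it contains no look at order that would show a problem.

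**Working it through.** **Inputs.** From the SAP Power Analysis: 50 matched pairs, two-sided 5%, standardised effect 0.41, power of at least 80%. From the design: half of each group is oxytocin-first. Assumed, because the documents give no value: L, the fraction of the oxytocin effect that remains at the second session. Effects for both aims are put on one standardised scale and the SD is held constant.

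**The plan's own figure.** Paired t-test, 49 df, noncentrality 0.41 × √50 = 2.90: power 81.1%, with 49 pairs needed for 80%. The stated power reproduces. It implicitly takes L = 0.

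**Order variation without carry-over.** Let π be the shift from first to second session. The within-person Aim 1b difference is E − π in desmopressin-first participants and E + π in oxytocin-first participants. The mean is unaffected by equal halves, but π² is added to the variance in each group. For Aim 1a the desmopressin-alone response is shifted by 0 or π, which adds π²/4 in each group. An order term removes this.

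**Aim 1b with carry-over.** Let E_P and E_C be the oxytocin effects in patients and controls. The oxytocin-first half loses L × E from the desmopressin-alone response, so the group mean loses L × E/2:

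contrast = E_P(1 − L_P/2) − E_C(1 − L_C/2)

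With L equal in both groups this is 0.41 × (1 − L/2):

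| L (assumed) | Effect | Power, 50 pairs | Pairs for 80% |
|---|---|---|---|
| 0 | 0.41 | 81% | 49 |
| 0.10 | 0.39 | 77% | 54 |
| 0.25 | 0.36 | 70% | 63 |
| 0.5 | 0.31 | 57% | 85 |

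**Aim 1a with carry-over.**

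contrast = 0.41 − (L_P × E_P − L_C × E_C)/2

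With E_P = E_C = 0.41:

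- L_P = L_C = 0.5: 0.41 − 0 = 0.41, power 81%. Equal absolute carry-over cancels.
- L_P = 0.5, L_C = 0: 0.41 − 0.1025 = 0.31, power 57%. Diluted.
- L_P = 0, L_C = 0.5: 0.41 + 0.1025 = 0.51, power 94%. Inflated.

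With equal L but a larger oxytocin effect in patients, as Aim 1b hypothesises, Aim 1a also shrinks. For example, E_P = 0.82, E_C = 0.41 and L = 0.5 give 0.41 − 0.5 × 0.41/2 = 0.31.

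**What a check could detect.** About 25 participants per group fall in each order. A 25 versus 25 comparison has 80% power only for a standardised difference of about 0.81. A first-session-only Aim 1a with 25 pairs, if order is matched within pairs (which the plan does not say), has 50% power at 0.41 and 80% power only at about 0.585.

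**The case against.** A reader might infer that carry-over is present and dilutes both aims. The documents do not support that. The sentence in Background 1.1 concerns effects on single neurons and gives no duration. The cerebrospinal fluid statement in Background 1.4 speaks of hours. Nothing describes an effect on the ACTH response a day later. The same section's description of desmopressin as longer-lasting does not help either: desmopressin is given in both sessions, so to first order its carry-over is a session effect that counterbalancing balances. Nor is the direction fixed for Aim 1a, as the three cases above show. A shorter interval in controls would by itself point to inflation.

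A reader might also infer that the groups are tested at different intervals and that this yields false-positive group differences. Separate days can be consecutive days, the Protocol says that control testing should reproduce patient conditions, and Table 1 and Figure 1 may settle the schedule. The restart rule for outpatients does not say whether a completed session is kept. A false-positive rate of 11% arises only if the oxytocin effect is equal in both groups (0.41), half of it persists in controls and none in patients (spurious difference 0.5 × 0.41/2 = 0.10). At L = 0.25 in controls only, the rate is 6.5%.

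Finally, first-session analyses are weak, and a null result would reassure nobody. That is correct, and it limits them to a supportive role.

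What remains is that order is part of the design and absent from the analysis, and that the available text gives an interval for one group only.

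**Conclusion.** The point holds as a gap in specification and is minor. About half of each group has the desmopressin-alone test after oxytocin, no order term or order-based check is planned, and the available text does not state the patients' between-test interval.

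The certain cost is avoidable session variation in both Aim 1 contrasts; its size is unknown. The possible cost is bias of unknown direction and size. For Aim 1b with equal L, power would be 77%, 70% or 57% at L = 0.10, 0.25 or 0.5, against 81% with none. Aim 1a would be unchanged if absolute carry-over were equal, smaller if patients carried over more, and larger if controls did. All of this rests on assumed values of L, equal halves by order and an unchanged SD. It does not show that carry-over occurs or that the two groups' schedules differ.

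**What to change.** 1. Reconcile the control wording in the Design Overview with the patient wording there and in item 4 of the in-hospital phase, so that one between-test interval rule applies to both groups. Record the actual interval for every participant. Which interval to use is for the investigators.
2. Include test order and a group-by-order term in the Aim 1a and 1b analyses, with the all-participant estimates kept as primary. Name the tests by type instead of day 1 and day 2. The order terms remove session variation and show whether the group contrast depends on order. They do not remove carry-over bias, which is why a common interval matters more than a test for carry-over.
3. Report second-session pre-dose ACTH and ratings by order and group; the Protocol already collects pre-dose values at each session.
4. Give first-session-only comparisons as supportive sensitivity analyses: patients versus controls among desmopressin-first participants for Aim 1a, and oxytocin plus desmopressin versus desmopressin alone, between participants within each group, for Aim 1b. State that with about 25 per order they are imprecise (50% power at 0.41 with 25 pairs) and that a null result does not rule out carry-over.

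The cost is some SAP wording, one scheduling sentence and one recorded variable, with no extra visits or samples. The SAP's closing section already reports a Phase 2 result. If Phase 1 testing is also complete, the intervals can only be tabulated by group, and the order analyses should be labelled as added afterwards.
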